7.0 STUDY DESIGN

This is a prospective, randomised, study with patients treated at multiple hospitals.

Prior to each surgeon enrolling their first study patient, they must be accredited to perform Stryker's Robotic-arm Assisted Surgery. Accreditation includes attending a Surgical Skills training course provided by Stryker and led by a surgeon experienced with using Mako, review of the planning and surgical technique guides, surgical observation and consultation with current Mako users.

All potential study patients will be assigned a MAKORCT-15 study ID.

If a patient has previously had a MAKO CT Arthrogram and wishes to participate in the study, the patient is required to sign the study approved consent form and the previous MAKO CT Arthrogram will be used for study purposes.

If the patient has previously had a MRI or MRI/CT Arthrogram (within 6 months of planned study surgery date), the patient is required to sign the study approved consent form and the previous MRI or MRI/CT Arthrogram will be used for study purposes. Once the study consent form is signed, the patient will be referred for a MAKO CT for surgical planning purposes.

If a patient has not had a MAKO CT Arthrogram, MRI or MRI/CT Arthrogram and wishes to participate in the study, the patient is required to sign the study approved consent form, and once signed the patient will be referred for a MAKO CT Arthrogram.

<http://ssp.intranet/sites/raqa/qms/documents/FM-CRD-029.docx>

MAKORCT-15 Final version 5.0 22 February 2018

If the patient meets the Inclusion and Exclusion criteria and has signed the study consent form, the patient will be enrolled onto the study. If the patient does not meet the Inclusion and Exclusion criteria and has signed the study consent form, the patient will be terminated from the study as a Screen Failure.

Enrolled patients will be randomised to one of two equally sized groups either; the Restoris® MCK Multicompartmental Knee System group or the Triathlon Primary Total Knee System group. Randomisation will take place via the Investigator or designee using the central randomisation system within Inform for allocation to either group. Block randomisation will be performed by a statistician using specialised randomisation software with a block size of 4.

Any deviation from the assigned treatment will be reported as a deviation from Protocol.

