12.2 Sample Size Justification

The change in the Oxford Knee Score (OKS) from pre-op to post-op assessments has a standard deviation of approximately 8.0 (Scott et al, SD=9.8; Walker et al, Table 2, SD=6 for UKR, and SD=8 for TKR). The parameters of the sample size calculation were set as follows: level of significance 0.05, 2-sided test, and postulated difference and standard deviation of 6.0 and 8.0 respectively. For these settings a sample of 29 patients in each arm is required to achieve a power of 80%. The sample size was increased by 20% to 35 in each arm, so 70 in total, in order to allow for withdrawals.

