12.4 Statistical Analysis

For each treatment group the demographic data will be summarised as number of observations, mean, standard deviation, minimum, median, maximum for continuous variables such as age, and as frequency and percentage for categorical variables such as gender.

For the test of the treatment effect the null hypothesis is no difference between the means of the 2 treatment groups, and will be tested against the alternative hypothesis that there is a difference between the means of the treatment groups.

The primary and continuous secondary efficacy variables will be analysed with a mixed model for repeated measurements (MMRM). The model will include factors for treatment group, time, and the interaction between treatment group, and time. For each variable the baseline values will be included in the model as covariate. The treatment effect will be tested against between patient variance. The time effect, and the interaction between treatment group and time will be tested against within patient variance. The results will be summarised as mean, and 95% CI by treatment group, and time. The least squares means will be reported for the treatment difference at each time, and overall with 95% CI. The results will be presented in tabular format, and graphically by treatment group, and time. The continuous variables of change from baseline, and percentage change from baseline will be reported as mean, and 95% CI for each treatment group.

Adverse events will be tabulated separately and reviewed for any commonalities.

The data will be summarised and comparisons presented according to:

<http://sspnet/sites/raqa/qms/documents/FM-CRD-029.docx>

MAKORCT-15 Final version 5.0 22 February 2018

- Treatment group : Restoris® MCK Multicompartmental Knee System or Triathlon Primary Total Knee System
- Adverse events: General complications, local complications, device-related complications, revisions/removals, loosening and pain.

In the event of errors in randomisation, the patient will be classified according to the treatment received. All randomisation inconsistencies will be listed.

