12.5 Analysis Populations

Intent to Treat Populations

An intent-to-treat analysis will be performed using all patients who were randomised and received a study device. Patients missing the measure of the primary end point (i.e. completed surgery and did not attend the 24 month visit) will be considered missing in the intent to treat analysis; no imputation of missing data will be conducted for any variables.

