17.2 Withdrawal from Study

Participants will be advised that they may voluntarily withdraw from the study at anytime, for any reason and they are not obligated to reveal the reason to the Investigator and it will not affect their medical care. However, in such cases, appropriate effort will be made to determine the reason for withdrawal from the study. The Investigator may request a letter from the patient noting his or her desire to withdraw from the study. All attempts to locate participants lost to follow up will also be documented.

Participants will be informed that should they withdraw from the study they should remain under the care of an appropriately experienced physician until the physician deems further follow-up unnecessary.

The following are circumstances for which a patient would be identified as not continuing their participation in the study:

- Study Completed / Terminated
- Screen Failure
- Death
- Unable to Return
- Unwilling to Return
- Concurrent Illness
- Lost to follow-up
- Re-operation of the affected knee joint, including revision of knee replacement components
- Incorrect implant(s)/device(s) used, device not included in protocol
- Other

Additionally, the patient may be withdrawn by the Investigator, if he/she is unable to continue participation in the study due to some condition unrelated to this study.

A Study Termination Form will be completed for all participants who withdraw from the study.

<http://ssp.intranet/sites/raqa/qms/documents/FM-CRD-029.docx>

MAKORCT-15 Final version 5.0 22 February 2018

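### Section 17.2 ends follow-up when an incorrect or non-protocol implant is used, a post-randomisation exclusion that can leave intent-to-treat patients with no post-operative OKS

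*Combined protocol and SAP*

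**What the plan says.** Four places in the combined protocol and SAP bear on a patient who does not receive the allocated implant.

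- **17.2 Withdrawal from Study** gives a list of circumstances in which participation does not continue. One is "Incorrect implant(s)/device(s) used, device not included in protocol". Nothing in the document provides for OKS collection after that point.
- **7.0 Study Design**: "Any deviation from the assigned treatment will be reported as a deviation from Protocol". It does not say whether the patient is followed.
- **12.4 Statistical Analysis**: "In the event of errors in randomisation, the patient will be classified according to the treatment received". The sentence is confined to randomisation errors.
- **12.5 Analysis Populations**: "An intent-to-treat analysis will be performed using all patients who were randomised and received a study device". A missing 24-month value stays missing, and nothing is imputed for any variable.

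The evaluation schedule in 1.0 places the first post-operative OKS at 6 weeks. Section 3.0 sets the primary comparison at 24 months. Section 4.0 provides for extra recruitment to make up for withdrawals and terminations.

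**The concern.** The implant is known when the operation ends, before any post-operative score exists. A patient ended at that moment has only a baseline OKS. The MMRM in 12.4 uses baseline as a covariate, so that patient contributes nothing to the treatment comparison, even if 12.5 counts the patient in the intent-to-treat set.

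This is an exclusion caused by something that happens after randomisation and may be related to the state of the knee. It may not fall equally on the two arms. Under 6.1 every patient is selected as a BKR candidate, with a functionally intact ACL and negligible lateral degeneration, the latter at the surgeon's discretion. An operative finding against those criteria would bear on BKR and not on TKR. If such knees leave one arm and their counterparts stay in the other, the arms are no longer comparable.

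Replacement recruitment under 4.0 restores the numbers but not the comparison. Safety counts may also be affected: 19.2 records serious adverse events until the patient is terminated from the study or 30 days after completion, so a later serious event, such as a revision, in an ended patient could go uncounted.

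**Working it through.** **1. The plan's own sample size.** Inputs from 12.2: "level of significance 0.05, 2-sided test, and postulated difference and standard deviation of 6.0 and 8.0 respectively". The plan concludes: "For these settings a sample of 29 patients in each arm is required to achieve a power of 80" per cent. For a two-sample t-test the noncentrality is d / (s × √(1/n₁ + 1/n₂)) with n₁ + n₂ − 2 degrees of freedom. At 29 per arm it is 6 / (8 × √(2/29)) = 2.86, and power is 80.1%; at 28 per arm power is 78.7%. The stated 29 reproduces (the normal approximation gives 28). Then "The sample size was increased by 20% to 35 in each arm, so 70 in total, in order to allow for withdrawals": 29 × 1.2 = 34.8, rounded up to 35. The sample size is not at fault on this point.

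**2. Who is ended by 17.2, on each reading.**

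| Patient | Narrow reading (second phrase explains the first) | Broad reading (two separate triggers) | Section 12.5 |
|---|---|---|---|
| Given the other arm's implant | Continues | Ended | In the intent-to-treat set |
| Given only a device outside the protocol | Ended | Ended | Not in the set |

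The first row is a conflict on the broad reading: the patient is in the analysis set but has no outcome. In the second row the sections agree, but they agree on excluding a randomised, operated patient.

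**3. Possible shift in the BKR mean.** Let p be the proportion of the arm lost and D the amount by which the lost patients would have scored below the rest. The full-arm mean is the retained mean minus p × D, so losing them raises the mean by p × D. The documents give neither p nor D; both are assumed here.

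- 2 of 35 lost (6%), D = 8: 2/35 × 8 = 0.46 points, which is 0.46/6 = 8% of the postulated difference.
- 5 of 35 lost (14%), D = 8: 5/35 × 8 = 1.14 points, or 1.14/6 = 19%.
- D = 0: no shift. D = −8: the same sizes in the other direction.

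For scale, the standard error of the arm difference at 35 per arm is 8 × √(2/35) = 1.91, so these shifts are 0.24 to 0.60 of a standard error.

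**4. Power if switched patients are lost or kept.** Allocation is 1:1 (7.0: "Enrolled patients will be randomised to one of two equally sized groups"). Assume that switching occurs only in the BKR arm at rate c, and that switched patients get no BKR benefit. If they are lost, BKR n = 35 × (1 − c) with the difference held at 6. If they are kept and analysed as randomised, n stays at 35 and the difference is 6 × (1 − c). With no other withdrawal:

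| c | BKR n if lost | Power if lost | Difference if kept | Power if kept |
|---|---|---|---|---|
| 0% | 35 | 87.1% | 6.0 | 87.1% |
| 5% | 33.2 | 86.3% | 5.7 | 83.6% |
| 10% | 31.5 | 85.3% | 5.4 | 79.5% |
| 20% | 28.0 | 82.9% | 4.8 | 69.7% |

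With 20% other withdrawal in both arms, power at c = 10% is 76.4% if lost and 69.9% if kept.

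**The case against.** The strongest reply is that 17.2 may not reach the case that matters most. If its second phrase defines the first, a BKR patient who leaves theatre with a Triathlon has received a protocol device and continues. The list also contains plain disposition labels (completed, screen failure, other), so it may partly be a set of reasons for the termination form. This stands as a reason for caution about the broad reading. It does not remove the point: the narrow reading still ends follow-up for a post-randomisation event, and sites could apply the bullet differently.

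A reader might infer that 17.2 contradicts 7.0 and 12.4. The documents do not support that. Section 7.0 asks only for a report and is silent on follow-up, and a surgeon's switch at operation is not a randomisation error under 12.4. The conflict is with 12.5. If 12.4 were applied to switches, a followed patient would be classified under TKR and leave the BKR mean anyway, so changing 17.2 alone would not be enough.

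A reader might also infer that the losses come mostly from BKR and bias the result towards it. Eligibility makes uneven loss plausible. But pre-operative MRI or arthrogram imaging is provided for, tricompartmental disease is excluded, and the documents describe no intra-operative conversion and give no rate or direction. The sign and size of D are also unknown.

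Finally, keeping these patients can lower power. That is correct and should be disclosed.

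**Conclusion.** The point holds in limited form. Section 17.2 contains a stated rule that ends follow-up because of the implant used. On either reading this is a post-randomisation exclusion that leaves no post-operative OKS; on the broad reading it also empties part of the intent-to-treat set in 12.5. Scores that were never collected cannot be recovered by later analysis.

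The size is not known. A shift of 0.5 to 1.1 OKS points rests on two assumptions, 2 to 5 of 35 lost from BKR and an 8-point deficit; it vanishes or reverses with D. The documents do not establish that every switched patient loses the 24-month score, that the loss is mainly in BKR, or that the result favours BKR. The loss of power from dropping these patients is small (87.1% to between 86.3% and 82.9% at 5% to 20% switching with no other withdrawal). The reason to act is to preserve the randomised comparison.

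**What to change.** - **17.2**: remove this bullet as a reason to end follow-up.
- **7.0 and 17.2**: state that a patient who receives any implant other than the one allocated is recorded as a protocol deviation and, unless the patient withdraws, completes the scheduled OKS and other visits to 24 months.
- **12.4**: replace classification by treatment received with analysis as randomised for efficacy, and list the implants actually received by arm.
- **12.5**: include all randomised, operated patients, whichever device was implanted.

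These changes concern data collection and analysis only; they leave the choice of implant and the patient's care as they are.

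Cost: wording changes in four sections and visits already in the schedule for what may be a handful of patients. The statistical downside is dilution. If switched patients get no BKR benefit, power at an assumed 10% switching in the BKR arm and no other withdrawal is about 79.5% with them kept, against 85.3% with them lost. The plan should acknowledge this.

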18.0 MODIFICATION OF PROTOCOL

No changes to this protocol will be permitted without the written approval of the applicable Ethics Committee.

Protocol deviation details, including the type of deviation (e.g. informed consent, inclusion/exclusion criteria, treatment, tests or visits not performed) should be recorded on a Protocol Deviation Form as soon as identified and notification will be made to the applicable Ethics Committee according to the Ethics Committee requirements.

19.0 DEFINITIONS AND REPORTING OF ADVERSE EVENTS

19.1 Definitions

Adverse Events:

Any undesirable clinical occurrence in a subject, whether it is considered to be device related or not, that includes a clinical sign, symptom or condition and/or an observation of an unintended technical performance or performance outcome of the device.

Expected: An adverse event is expected when the specificity and severity of the event is consistent with a complication that is not related to the device but may be related to the surgical procedure.

Unexpected: An adverse event is unexpected when the specificity or severity of an adverse event is not consistent with the standard. It refers to an adverse event that has not been observed before.

Adverse Device Event

A clinical sign, symptom or condition that is causally related to the product, implantation procedure, the presence of product or the performance of the device system.

Serious Adverse Advent (SAE):

Any untoward medical occurrence that:

<http://ssp.intranet/sites/raqa/qms/documents/FM-CRD-029.docx>

MAKORCT-15 Final version 5.0 22 February 2018

- Results in death,
- Is life threatening,
- Requires inpatient hospitalization or prolongation of hospitalization*,
- Results in persistent or significant disability/incapacity,
- Is a congenital anomaly/birth defect, or;
- Is a medical or surgical intervention to prevent life-threatening illness and injury or permanent impairment to a body structure or a body function.

*Planned (elective) hospitalization for a preexisting condition (a condition that is captured on the pre-op clinical data/medical history CRF), or a procedure required by the protocol, without serious deterioration in health, is not considered a Serious Adverse Event for this study.

Examples of such elective procedures include, but are not limited to, the following commonly seen events:

- Contralateral Total Knee Replacement or Partial Knee Replacement
- Total Hip Replacement
- Cataract Surgery

Such events should not be categorized as SAEs on the Stryker AE/SAE Reporting Form, but rather should be classified as Adverse Events.

Cancer should be captured as one SAE per diagnosis. All related follow up treatments for the primary cancer diagnosis, including in-patient Chemotherapy or Radiotherapy should be captured as new information for the same SAE (the SAE can be left as unresolved with status date changed each times updates are made to the treatment section.) All metastasized (secondary) cancer diagnoses and associated treatments should be captured on a new SAE form.

19.2 Reporting of Events

CONFIDENTIAL

MAKORCT-15

Any serious adverse event that occurs between patient consent and end of study, or adverse event that occurs from surgery to end of study will be recorded as such.

Additionally, any adverse event identified during radiographic review, will be recorded as such.

Adverse Events:

Any adverse event should be recorded as follows:

All information on general medical, operative and device related complications (adverse events) will be documented on Case Report Forms (CRFs) or electronic Case Report Forms (eCRFs). Information should include date of occurrence, description, severity, relationship to study device, treatment and date of resolution.

The Investigator must determine if the event is related to the device. Any adverse event in a study patient must be monitored until the event is resolved or considered non-clinically significant by the Investigator.

Expected Events: Should be reported to the Sponsor soon as possible, but not later than ten working days after the Investigator first learns of the effect.

Adverse Device Events

Should any adverse device events occur, the study staff will ensure that these are documented by the Investigator and reported immediately to the Sponsor. They should also be reported to the reviewing Ethics Committee and Institution as soon as possible, but not later than fifteen working days after the Investigator first learns of the effect, unless an earlier timeline is specified by individual study sites. The Investigator with the Sponsor will conduct an evaluation of such effects. Following this evaluation, if the Investigator determines that an unanticipated adverse device effect presents an unreasonable risk to participants, the Investigation will be terminated as soon as possible. Termination shall occur no later than five working days after the Investigator makes this determination and

<http://sspintranet/sites/raqa/qms/documents/FM-CRD-029.docx>

MAKORCT-15 Final version 5.0 22 February 2018

CONFIDENTIAL

MAKORCT-15

no later than fifteen working days after the Investigator first receives notice of the unanticipated adverse effect.

Serious Adverse Events:

Any adverse event that is considered to be of serious nature and occurs at any time point from the signing of Informed Consent Form until either the patient is terminated from the study, or 30 days post-completion, should be recorded as follows:

All Serious Adverse Events (SAEs) should be reported immediately to the Sponsor by email or fax, **no later than 24 hours** after becoming aware of the event. The immediate reports should be followed promptly by detailed, written reports. Reports should identify subjects by unique code numbers assigned to the trial subjects rather than by the subjects' names and/or addresses. The Investigator should also comply with the applicable regulatory requirement(s) related to the reporting of serious unexpected adverse device reactions to the regulatory authority (TGA) and the Ethics Committee. All other SAEs that are NOT related to the device will be reported to the Ethics Committee in a table with the annual reports, or as otherwise directed by the relevant Ethics Committee.

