6.2 Exclusion Criteria

1. The patient has a clinically deficient ACL and cruciate and collateral ligament insufficiency on MRI or MRI/CT Arthrogram.
2. The patient is undergoing revision surgery
3. The patient has greater than 10° of hyperextension, greater than 10° of varus or valgus deformity, greater than 10° Flexion Contracture
4. The patient has active, local infection or previous intra-articular infection
5. The patient has skeletal immaturity
6. The patient is without sufficient bone stock to allow appropriate insertion and fixation of the prosthesis

<http://ssp.intranet/sites/raqa/qms/documents/FM-CRD-029.docx>

MAKORCT-15 Final version 5.0 22 February 2018

7. The patient's weight, age or activity level might cause extreme loads and early failure of the system (surgeons discretion).
8. The patient has a systemic or local condition that would limit the ability to assess the performance of the device e.g. neuromuscular or neurosensory deficiency, disorder leading to progressive bone deterioration (including rheumatoid arthritis and osteoporosis), or patient is immunologically suppressed.
9. Patient has a cognitive impairment, an intellectual disability or a mental illness that is considered by the investigator to inhibit the patient's capacity to consent to research and the ability to participate in it
10. Patients with tricompartmental disease are contraindicated from the study

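### Non-serious adverse events are recorded only from surgery, so non-serious harms of the CT arthrogram that the trial orders after consent have no adverse event record

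*Combined protocol and SAP*

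**What the plan says.** Section 19.2 (Reporting of Events) sets two starting points. Serious events are covered by "Any serious adverse event that occurs between patient consent and end of study". For all others, an "adverse event that occurs from surgery to end of study will be recorded as such". The evaluation schedule in Section 1.0 matches: the Serious Adverse Events row is ticked from History/Pre-Op, while the Adverse Events row has no tick there and begins at Intra-Op.

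Later in the same section, the detailed rule for serious events gives a different end point: "from the signing of Informed Consent Form until either the patient is terminated from the study, or 30 days post-completion".

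Section 7.0 (Study Design) deals with a patient who has no earlier MAKO CT arthrogram, MRI or MRI/CT arthrogram. That patient signs the consent form, and "once signed the patient will be referred for a MAKO CT Arthrogram". The footnote to the schedule makes the same distinction by earlier imaging. For a consented patient who fails the selection criteria, Section 7.0 says that "the patient will be terminated from the study as a Screen Failure".

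**The concern.** The trial itself orders the arthrogram, for a defined group of patients, after they have consented. In its usual meaning an arthrogram involves contrast placed in the joint, here the knee that is to be operated on. One would expect the harms of a procedure done at the trial's direction to be recorded in the trial's safety data. With the window as written, staff who follow the plan exactly will not record the non-serious ones.

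The gap is widest for screen failures. They may have the procedure and gain nothing further from the trial. No study surgery follows, so they have no non-serious event window at all, and it is unclear how long their serious events are followed.

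**Working it through.** No sample size, power or event figure in the plan bears on this point. The check sets the recording windows beside the imaging pathway.

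| Event type | Window in Section 19.2 | Schedule row | Arthrogram (after consent, before surgery) |
|---|---|---|---|
| Non-serious | Surgery to end of study | No History/Pre-Op tick; starts Intra-Op | Outside |
| Serious | Consent to an end point given in two ways | Ticked from History/Pre-Op | Inside, while the patient stays in the study |

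1. **Where the arthrogram falls.** Section 7.0 places it after consent. Section 14.0 makes the person a trial patient on signing. Exclusion criterion 1 in Section 6.2 draws on MRI or arthrogram findings, so the imaging feeds eligibility and comes before randomisation.

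2. **Whether the definition excludes these events.** It does not. Section 19.1 defines an adverse event without regard to device relationship and does not tie it to surgery. Only the time window keeps the events out.

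3. **Whether another route records them.** Section 19.2 adds that "any adverse event identified during radiographic review, will be recorded as such", with no start date. That can pick up what an image shows, but not pain or a reaction after the procedure. Section 11.0 promises to document complications generally, but refers to Section 19.0 for handling, which leads back to the surgery start.

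4. **Screen failures.** The non-serious window needs surgery, so for them it is empty. For serious events there are two readings:
   - Opening sentence of 19.2: consent to end of study.
   - Detailed rule in 19.2: consent to termination. The 30-day extension attaches to completion, which a screen failure does not reach, so nothing follows termination.

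5. **Size.** The number exposed among the 70 planned patients is 70 × p, where p is the share without earlier imaging. The documents do not give p. Purely as an assumption, p = 0.25 gives 70 × 0.25 = 17.5 (about 18), and p = 0.75 gives 70 × 0.75 = 52.5 (about 53). Screen failures who had the arthrogram come on top, and their number is not stated. These are counts of exposed patients. Missed events would be the number exposed times an event rate, and the documents give no rate, so that number cannot be calculated.

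6. **Effect on the comparison of arms.** The arthrogram precedes randomisation, and the recording rule is the same in both arms. The primary Oxford Knee Score comparison does not use these data, and the between-arm comparison of adverse events should not be biased.

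**The case against.** The strongest reply is that this is a deliberate choice. The schedule and Section 19.2 agree on the surgery start, this is a phase IV study of approved devices, and collection begins with the treatment under study. Serious harms are already recorded from consent. Section 13.0 obliges investigators to provide care for trial-related adverse events, and under Section 16.0 monitors look for complications not yet documented. What is missing is a data line, not care.

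Most of that stands. It limits the point to completeness of safety data, but it does not supply the missing record: a consistent rule can still leave out the non-serious harms of a study procedure.

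Several stronger readings are tempting, and the documents do not support them:

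- *A joint infection treated without admission would be lost.* The seriousness criteria in Section 19.1 include intervention to prevent permanent impairment, so a treated joint infection may well qualify as serious and be recorded from consent.
- *The trial's infection screen is weakened.* The exclusion criterion "The patient has active, local infection or previous intra-articular infection" works through the pre-operative review of criteria in Section 14.0, not through the adverse event form.
- *A later infection could not be traced to a pre-operative cause.* Section 11.0 also collects relevant medical history before surgery. At most, a dedicated adverse event entry is absent.
- *Pre-operative serious events have no analysis population.* Section 12.5 defines the intent-to-treat analysis as "using all patients who were randomised and received a study device". It does not restrict safety listings. Section 12.4 tabulates adverse events separately, and Section 19.2 sends serious events unrelated to the device to the Ethics Committee with the annual reports, or as that committee directs.
- *Screen failures leave collection straight after the arthrogram.* No interval between imaging and termination is given, and the opening sentence of Section 19.2 points to a later end.

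**Conclusion.** The concern holds for non-serious events of the trial-ordered arthrogram. They occur after consent and before surgery, so the plan as written gives them no adverse event record. Serious events of the procedure are recorded while the patient remains in the study, so it would be wrong to infer that arthrogram harms in general go uncaptured.

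For screen failures, non-serious events are never recorded, and the end of serious-event recording depends on which sentence of Section 19.2 is followed. That contradiction needs resolving in its own right.

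The conclusion rests on the text alone. It applies to patients without earlier imaging; the others have a MAKO CT or reuse a previous arthrogram. The range of about 18 to 53 of 70 shows exposure under an assumed share and is not an estimate of harm; the number of missed events could be very small. The gap merits an amendment because it concerns a study procedure and is cheap to close. It does not threaten the primary result.

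**What to change.** - In Section 19.2 and the evaluation schedule, start adverse event collection at consent, or at the trial-ordered arthrogram if the sponsor wants to limit it to trial procedures. Add an Adverse Events tick in the History/Pre-Op column.
- Reconcile the two end points for serious events in Section 19.2, so that screen failures who had a trial-ordered arthrogram are covered for the existing 30-day period. State the date from which the 30 days run.
- In Section 12.4, add a listing of pre-operative adverse and serious adverse events for all consented patients, separate from the post-surgery tables so that the between-arm summaries are unchanged.

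The cost is amendment wording, one tick and one listing. In practice it means a few more adverse event forms and one contact with each screen failure who had the arthrogram.
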